12.5 Emergency Procedures

In the event of a medical emergency (i.e., an event that requires Taiwan's immediate attention regarding the treatment of the subject, operation of the clinical study, and/or use of study drug), study site personnel will immediately contact the Medical Monitor.

The investigator will ensure that all study site personnel responsible for the subject's medical care are familiar with the Medical Emergency Call number, its location and have access to it.

Prior to the start of dosing at the site, the Clinical Monitor will review medical emergency call procedures with study personnel.

12.5.1 Emergency Decoding

As each subject is randomized into the study, his/her treatment assignment will be individually determined using IVRS/IWRS. This information will be kept in a secured fashion.

In the event of a medical emergency when knowledge of the subject's treatment assignment would influence the subject's clinical care, the principal investigator must contact the Medical Monitor to describe the emergency. Only under these circumstances will TaiwanJ and/or Medical Monitor authorize unbinding of the subject's treatment assignment.

If a subject's treatment assignment is unblended for a medical emergency or for regulatory purposes, that subject must immediately and permanently discontinue treatment with study drug but should remain in the study and continue the protocol specified follow-up evaluations.

If a subject's treatment assignment is accidentally unblended, that subject should continue treatment with study drug and remain in the study. The data will be included in the intent-to-treat data set.

The investigator must document the reasons for the unbinding in the subject's CRF and is strongly encouraged not to divulge the subject's treatment assignment to any individuals not directly involved in managing the medical emergency.

13. STATISTICAL CONSIDERATIONS

13.1 Sample Size Calculation

The study will need to screen approximately 100 subjects to enroll 60 patients with biopsy-proven NAFLD who meet the study inclusion / exclusion criteria. With 20 subjects per treatment group, the study will not be powered for efficacy assessment between the two doses. Based on precision analysis, the proposed sample size will provide the maximum error (defined as the half-way of the width of the 95% confidence interval for the difference (change in liver-biochemistry) between two doses (5 mg twice daily vs 10 mg twice daily dose) allowed.

Presuming the observed difference between two treatment groups is 20%, then the 95% confidence interval for the true mean is given by (2.5%, 37.5%) with 20 subjects in each group.

13.2 General Statistical Methodology

Prior to database lock, a final detailed Statistical Analysis Plan (SAP) will be available. Results, when available, will be summarized into tabulations, case listings, plots, and histograms for comparison.

Three major study populations are planned, modified intent-to-treat (met) population, per protocol (PP), and safety populations.

Baseline variables will be ascertained for conformity among all stratification factors. All baseline analysis will be based on the met population. In the met population, the subjects will be counted in the treatment group to which they were randomized, as long as they received at least one dose of study medication and have at least one return visit.

The safety analysis will be based on the safety population. In the safety population, subjects will be counted in the group in which they were treated. To assess the robustness of the study outcomes, a sensitivity analysis will be performed on all pertinent major efficacy variables. The sensitivity analysis will include and exclude patients with major study deviations and early withdrawals to assess the impact on the study endpoints.

The criteria may be amended prior to unbinding of the treatment assignment for the analysis of data. Reasons for changes may include study conduct changes, protocol amendments, or changes in the appropriateness of the criteria, which may be assessed based on review of blinded data.

For all analyses, all missing values due to patient early termination from the study will be not imputed.

For each patient, the Baseline values will be defined as those values recorded at Day 1 prior to dosing or Screening, as appropriate.

All hypotheses will be tested for statistical significance with two-tailed p-values. Results of all tests will be considered statistically significant if their p-value is less than or equal to 0.05, except for results of the tests for interaction will be considered statistically significant if the p-value is less than or equal to 0.10.

13.2.1. Analysis of Continuous Variables

Continuous variables will be summarized with descriptive statistics (i.e., sample size, mean, standard deviation, minimum, maximum, median, and quintiles). The continuous variables will be analyzed using a general linear model to test the treatment effect of the changes from pre- to post-treatment [29].

If the data are not transformable to symmetry, rank methods such as the Friedman rank test will be used. The possible transformation will be applied on the original pre- and post-treatment values only.

13.2.2. Analysis of Categorical Variables

Categorical variables will be summarized with descriptive statistics (i.e., sample size, frequency counts, percentage, and 95% confidence interval) and will be analyzed with CMH test adjusting for tumor size [30].

13.2.3. Analysis of Time-to-Event Variables

Time to event variables (such as time to treatment success) will be assessed by survival analysis. The cumulative portion of the time-to-event variables of each treatment group will be determined by Kaplan-Meier estimates. Fisher's exact or chi-square test will be used to compare the portion of patients with the event occurring at different time intervals throughout the study period.

When it is beneficial, a more precise comparison of the treatment effects will be analyzed by fitting a Cox proportional hazard model to assess the benefit-risk ratio.

13.4. Analyses

13.4.1. Efficacy Analyses

13.4.1.1. Primary Efficacy Endpoint

The primary endpoint of this study is assessment of safety and the change in hepatic steatosis as measured by MRI.

13.4.1.2. Secondary Efficacy Endpoint

The secondary endpoints of this study are:

- Time to remission (TTR) is defined as time, in weeks, from randomization to liver function remission as defined as two consecutive ALT values within normal range (< 40 IU/mL) during study period. The Cox proportional hazard model with treatment and diabetes status as factors, will be used.
 - ALT changes from baseline. The statistical analysis will be the same as the one used for the primary efficacy endpoint
 - Changes in metabolic markers and NASH related biomarkers

13.4.2. Timing of Analyses

- All endpoints will be analyzed at the time point when all subjects have completed the treatment program and at the time when all subjects have completed the study.

13.4.3. Safety Analyses

13.4.3.1. Primary Safety Endpoints

The rate of patients by treatment groups who experience (1) one or more adverse events (AEs); (2) SAEs; and, (3) AEs leading to discontinuation of study medication (4) adverse events in each grade of the Common Terminology Criteria for Adverse Events (CTCAE) v3.0, published by the National Cancer Institute will be displayed. Treatment effect will be explored by inspection of observed rates for the dose groups within each treatment regimen.

Adverse events will be summarized in frequency counts by treatment group using current Medical Dictionary for Regulatory Activities (Mudra) terms. Summaries of AEs will be displayed:

1. All AEs by system organ class regardless of the relationship to the study treatment;
2. By treatment relationship (“possible, probable or definite” related vs. not related); and
3. By maximum severity (mild, moderate, or severe).

13.4.3.2. Other Safety Endpoints

Change from Baseline for each interval-valued laboratory test, vital signs, and other safety related variables will be summarized regarding each scheduled visit. Shift tables will be presented for laboratory values based on the central laboratory normal ranges.

All abnormalities deemed clinically significant by the investigator will be presented in detail and listed by patient identifier. The patients who have no laboratory results at the Screening or post-Baseline visit will be excluded from the change from Baseline and shift table analyses. Treatment effect will be explored by inspection of observed means or rates for the dose groups within each treatment regimen.

13.4.4. Sensitivity Analysis

Sensitivity analyses of the primary efficacy variable will be conducted as described below to assess the robustness of the primary analysis results. In the sensitivity analysis, decreases in p-values due to drops in power (decreasing sample sizes and increasing standard errors) will be distinguished from changes in the effect size. The criterion that defines substantial changes will be those changes that alter the effect parameter by more than one standard error.

The sensitivity analysis will use the following algorithm:

1. Subjects who are excluded from per protocol population and subjects who withdraw from the study at or after interim analysis will be considered as a responders or non-responders at the end of the study according to their response status at the time of withdrawal.
2. Subjects who drop out at the time are considered as non-responders at the time of withdrawal. Subjects who withdraw early, regardless of their final outcomes, will be considered as non-responders at the end of study
3. Remaining patients assigned to treatment will be considered as responders at the end of study if the withdrawals occur at the end of the study and they are also responders

at the time of withdrawal and at the last visit prior to the withdrawal. Remaining JKB-121 patients who drop out of the study at or after interim analysis will be considered as JKB-121 non-responders at the end of the study if they don't satisfy the described above.

4. Sensitivity analysis will be performed to assess the impact of patients with significant protocol violations possibly leading to improved efficacy, e.g. use of concomitant medications. Definitions of significant protocol violations will be described in detail in the statistical analysis plan before the study blind is broken.

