13.5 Interim Analysis Plan

No interim analysis is planned for this study,

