## 5 EFFICACY ENDPOINTS

### 5.1 Primary Efficacy Endpoint

Mean and absolute changes from baseline in the percentage fat content of the liver measured by magnetic resonance imaging (MRI) at week 24.

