## 6.9 Efficacy Analysis

### 6.9.1 Primary Efficacy Endpoint

The change from baseline at Week 24 of the percentage fat content of the liver measured by MRI will be analyzed by analysis of covariance (ANCOVA) in the Full Analysis Set Population with treatment group and diabetes stratum as factors and baseline MRI value as a covariate. The comparisons will be (1) between the response of the JKB-121 5 mg group and the response of the Placebo group and (2) between the response of the JKB-121 10 mg group and the response of the Placebo group. The least-squares means, standard errors, and 95% confidence intervals for each treatment group and for each comparison will be provided. The two-sided p-values testing for significance within treatment group change from baseline and comparisons between treatment groups will be presented. No multiple comparisons techniques will be applied. The sample SAS code can be found below:

```
*****
Note:
  TREATMENT = 0, (placebo), 1 (JKB-121 5 mg), 2 (JKB-121 10 mg)
  DIABSTAT = nondiabetic, diabetic
  BASE: baseline percentage fat content of the liver measured by MRI
  CHG: change from baseline to Week 24 in the percentage fat content of
       the liver measured by MRI
*****;
proc glm data=MRI;
  class TREATMENT DIABSTAT;
  model CHG = TREATMENT DIABSTAT BASE / ss1 ss3;
  means TREATMENT;
  lsmeans TREATMENT / cov stderr pdiff cl;
  estimate "JKB-121 5 mg : Placebo" TREATMENT -1 1 0;
  estimate "JKB-121 10 mg : Placebo" TREATMENT -1 0 1;
run;
```

The data and model residuals will be inspected for normality and homogeneity of variance, and a logarithmic transformation will be applied if necessary.

To handle missing results such as due to early termination, multiple imputation will be performed. The detailed steps are specified below.

Step 1: Prepare the data for multiple imputation. Since there is only one intermediate visit (Week 12) for MRI collection, the missing pattern would be monotone if endpoint values are not available.

Step 2: PROC MI would be used to impute the missing MRI values. The treatment, diabetes stratum, and MRI values at baseline and all available post-baseline visits would be included. The SAS code can be found as below:

```
PROC MI data=MRI out=MI_OUT nimpute=1000 seed=12345 minimum=0;  
  var TREATMENT DIABSTAT BASE WEEK12 WEEK24;  
  mcmc initial=em prior=jeffreys nbiter=200 niter=500 chain=single;  
run;
```

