### **Responder Analysis**

The number and percentage of responders will be provided by treatment group. A subject who had as two consecutive ALT values within normal range during the treatment period will be defined as a responder. Subjects who are not responders and early withdraw will be considered as non-responders. Cochran-Mantel-Haenszel statistics will be provided adjusting for diabetes stratum.

```
*****  
Note:  
  TREATMENT = 0, (placebo), 1 (JKB-121 5 mg), 2 (JKB-121 10 mg)  
  DIABSTAT = nondiabetic, diabetic  
  RESPONDER: Y/N responder  
  COUNT: number of subjects  
*****;  
proc freq data=ALT;  
  tables DIABSTAT*TREATMENT*RESPONDER / cmh;  
  weight COUNT;  
run;
```

Sensitivity analyses will be conducted using subjects who complete the study.

Similar summaries and analyses will be provided for:

- Subjects whose ALT level at each scheduled visit during the treatment period is within normal range.
- Subjects whose ALT level is within normal range at any time within the following time intervals which will be derived using actual study days:
  - a. Baseline to Week 12

b. Week 12 to Week 24

- Subjects achieving a 20% reduction from baseline at any time during the treatment period.

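### Steps 1 to 3 of the Protocol 13.4.4 sensitivity algorithm cannot be run for the MRI endpoint, and no planned MRI analysis departs from missing at random

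*Protocol*

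**What the plan says.** **Sensitivity plan.** Protocol 13.4.4 opens: "Sensitivity analyses of the primary efficacy variable will be conducted as described below to assess the robustness of the primary analysis results". Step 1 covers "subjects who withdraw from the study at or after interim analysis" and classes each of them as a responder or non-responder by the status held on leaving. Step 2 counts early withdrawals as non-responders. Step 3 gives responder rules for the remaining subjects, and its last sentence applies an interim-based rule to JKB-121 dropouts only. Step 4 examines significant protocol violations and leaves their definition to the SAP. The section treats a change as substantial if it moves the effect by more than one standard error.

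**Interim.** Protocol 13.5: "No interim analysis is planned for this study".

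**Endpoint and responder.** SAP 5.1 defines the primary endpoint as "Mean and absolute changes from baseline in the percentage fat content of the liver measured by magnetic resonance imaging (MRI) at week 24". The SAP defines a responder under Responder Analysis (6.9.2.1), on ALT: "A subject who had as two consecutive ALT values within normal range during the treatment period will be defined as a responder".

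**Missing data.** Protocol 13.2: "For all analyses, all missing values due to patient early termination from the study will be not imputed". The same section plans a general sensitivity analysis with and without major deviators and early withdrawals. SAP 6.9.1: "To handle missing results such as due to early termination, multiple imputation will be performed". Its imputation model contains treatment, diabetes stratum, and baseline, Week 12 and Week 24 MRI. The analysis is repeated in the mITT population, and in the Per Protocol population without imputation.

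**The concern.** The protocol commits to testing the robustness of its primary result, but most of the stated method does not fit this trial. It needs a binary response that the MRI endpoint does not have, and a calendar event that will not occur. The SAP neither repairs nor mentions it.

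Withdrawal here can follow ALT rises or adverse events (Protocol 6.3, 10.4.7, 12.4), so missing scans may be related to drug and outcome. ALT and the reason for withdrawal are not in the imputation model. With 20 subjects per arm and no dropout allowance in the sample size, a few missing Week 24 scans carry weight. A reader of the final report would want to know how far the MRI result depends on the assumption made about those subjects.

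**Working it through.** **1. Can the algorithm be run?**

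| Part of Protocol 13.4.4 | What it needs | What the documents provide |
|---|---|---|
| Step 1 | Responder status; interim date | No MRI cut-off; no interim (13.5) |
| Step 2 | Responder status | No MRI cut-off |
| Step 3 | Responder status; interim date | Neither; last sentence names JKB-121 dropouts only |
| Step 4 | Definition of significant violations | Can be run once defined; SAP 6.3.4 refers to major violations without defining them |

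**2. What does the SAP offer for MRI?** Its labelled sensitivity analyses cover other endpoints: completers for the ALT responder analysis, and a repeated-measures model for AST, ALT and GGT. For MRI there are three analyses:

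- Full Analysis Set and mITT with multiple imputation: both assume missing at random given the model variables.
- Per Protocol without imputation: subjects without a Week 24 MRI are left out. So are subjects who did not complete treatment and major violators, so a difference from the Full Analysis Set cannot be attributed to missing-data handling alone.

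The include/exclude plan in Protocol 13.2 adds little for these subjects. Under that section's no-imputation rule, a subject without a Week 24 scan contributes nothing to a Week 24 ANCOVA, whether nominally included or not.

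**3. How large could the effect be?** Inputs from SAP 6.1: 20 per group, a difference of about 5 (read here as percentage points of liver fat), about 85% power. Two-sided alpha of 0.05 is from Protocol 13.2. No SD and no dropout rate are given.

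*The plan's figure.* The 85% cannot be reproduced without an SD. Solving backwards gives an SD of 5.28 (normal approximation) or 5.14 (t-test). Taking 5.14:

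- SE = 5.14 × √(2/20) = 1.63 points.
- Smallest significant difference = 2.024 × 1.63 ≈ 3.3 points (38 df).

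*Illustration.* Suppose a share m of one active arm has no Week 24 MRI and all of them have the placebo mean. Then effect = 5 × (1 − m), and shift = 5 × m.

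| m (assumed) | Effect | Shift | Shift / SE |
|---|---|---|---|
| 10% | 4.50 | 0.50 | 0.31 |
| 15% | 4.25 | 0.75 | 0.46 |
| 20% | 4.00 | 1.00 | 0.61 |
| 30% | 3.50 | 1.50 | 0.92 |

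The SD is also an assumption. At 15% to 20% missing, an SD of 4 (SE 1.26) gives 0.59 to 0.79 SE, and an SD of 8 (SE 2.53) gives 0.30 to 0.40 SE.

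*Smaller observed effects.* With the SE held at 1.63, an observed effect loses significance under this scenario if it lies between 3.3 and 3.3/(1 − m). The upper limit is 3.3/0.85 ≈ 3.9 at 15% and 3.3/0.80 ≈ 4.1 at 20%.

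*Tipping point.* The mean shift among missing subjects that moves a 5-point effect by one SE is 1.63/m: 16.3, 8.1 and 5.4 points at 10%, 20% and 30% missing. The shift that loses significance is (5 − 3.29)/m: 17.1, 8.5 and 5.7 points.

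**The case against.** The other side has a good deal to say.

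- **Follow-up continues off drug.** Protocol 6.1, 10.1 and 10.4.4 seek Week 24 assessments, including MRI, from subjects who stop treatment, and the Full Analysis Set keeps them. If they drift back towards placebo and attend, their observed scans already dilute the effect. This stands: the point concerns only subjects with no Week 24 MRI.
- **The imputation uses Week 12 MRI.** A reader might infer that dropouts are assumed to have kept responding. The model does not say that: a subject with no response at Week 12 is not simply imputed as a continuing responder.
- **There are other analyses.** A reader might infer that the SAP puts nothing in place of 13.4.4 and that robustness to dropout goes untested. The documents do not support that. Imputed against non-imputed results give a limited check, and Protocol 13.2 plans an include/exclude comparison.
- **Part of 13.4.4 survives.** Step 4 needs neither a responder nor an interim, and the rule counting early withdrawals as non-responders reappears in the SAP for ALT, where a responder exists. The failure is confined to steps 1 to 3 as applied to MRI.
- **The trial is exploratory, with 60 subjects.** This argues for a modest remedy. It does not excuse keeping a prespecified check that cannot be carried out.

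**Conclusion.** The point holds in a limited form. Steps 1 to 3 of Protocol 13.4.4 cannot be applied to the MRI endpoint, the SAP drops them without explanation, and no planned MRI analysis departs from missing at random for subjects without a Week 24 scan. This conclusion comes from the text and needs no assumed numbers.

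The size does rest on assumptions: missing rates of 15% to 20%, every missing active-arm subject at the placebo mean, and an SD of about 5.14 that is only implied by the 85% power. The loss is then 0.75 to 1.0 point, about 0.5 to 0.6 SE. A reader might infer that a true 5-point result would be overturned. On these figures it would not: the shift is below the protocol's one-SE criterion, and 4.0 to 4.25 exceeds the 3.3 points needed for significance. The exposure is an observed effect between about 3.3 and 4.1 points, where no planned analysis would show the dependence on the missing-data assumption.

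**What to change.** 1. Delete steps 1 to 3 of Protocol 13.4.4. Keep step 4, and define the significant protocol violations in the SAP as that step promises.
2. Before unblinding, prespecify in SAP 6.9.1 at least one rerun of the imputation for subjects with missing Week 24 MRI: a delta-adjusted tipping-point series for the active arms, a control-based imputation in which those subjects follow the placebo distribution, or both.
3. Analyse these reruns on the Week 24 value itself. Step 3 of SAP 6.9.1 averages Week 12 and Week 24, so a delta added to Week 24 alone would move that average by only half. Step 3 should be reconciled with the Week 24 endpoint first.
4. Reconcile the no-imputation rule in Protocol 13.2 with the multiple imputation in SAP 6.9.1, stating which governs the primary analysis.

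The cost is a short SAP paragraph, a matching protocol edit, and modest extra programming and reporting. A delta series can use the imputed data sets already planned; control-based imputation needs somewhat more code. No new data are required.

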13.5 Interim Analysis Plan

No interim analysis is planned for this study,

13.6 Medical Monitoring and Independent Data Review Board

A Medical Monitor, independent of TaiwanJ Pharmaceuticals, will be appointed to monitor safety and efficacy of the study. The medical monitor will be a hepatologist experienced in clinical trials in the field of NASH. The medical monitor will have statistical expertise and/or access to biostatistician with the contacted CRO to monitor safety as assess reported adverse events. An independent Data Review Board consisting of a hepatologist and biostatistician unblinded to treatment allocation will be compiled to assess safety events in treatment groups as compared to placebo.

